DBS optimization: Three weeks after the neurostimulator is implanted, we will optimize the DBS settings. DBS titration will be based on stimulation parameters used in previous OCD and SUD studies [101, 144-146]. We will start by screening each contact for clinical effect guided by craving scores and side effects such as photopsia (optic tract), tetanic contraction (posterior limb of internal capsule), or behavioral change (anterior limb of internal capsule). While it is unclear if LP DBS results in acute effects on alcohol craving, we will attempt to optimize DBS settings while measuring craving using the ACQ-SF-R questionnaire and Cue Reactivity task (we will monitor for acute changes in craving scores on the ACQ-SF-R and CR scales with the different DBS settings). If no clear clinical effect is observed, we will identify the optimal electrode contact and stimulation parameters using Lead-DBS software [147, 148]: we will 1) reconstruct and localize the electrodes and 2) simulate the VTiA at different contacts as described in our previous study [69]. DBS will be turned ON in a standard monopolar mode at 135 Hz at the primary and other DBS contacts while monitoring for side effects. We will use pulse width 90-150 μ s and intensity 2-6 V, which proved to be the most effective in OCD and SUD DBS studies [101, 144, 145]. We will use symmetric biphasic pulses, shown to be more efficacious in ameliorating PD and tremor symptoms than other configurations [37, 149-151]. Stimulation intensity will be increased in small increments until we observe side effects or a voltage limit of 10V, whichever is lower, which will be considered the ceiling of stimulation. We will then reduce stimulation intensity to 70% of ceiling voltage.

DBS titration will occur over the course of 2 days. After optimization, DBS will be turned ON continuously at the optimized settings. We will continue to titrate the DBS settings during follow-up visits if participants experience delayed AE or continue to crave and relapse.

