8.1 Reasonably Foreseeable Risks Related to Study Device

More than 208,000 DBS systems have been implanted thus far, the majority for fully FDA-approved indications, including PD, epilepsy, and essential tremor, or for Humanitarian Device Exemption indications, including obsessive compulsive disorder (OCD) and dystonia. The safety profile of DBS continues to improve, however there remains a certain level of risk to patients. In a systematic review of 52 DBS studies, including 2249 patients total, between 2008 and 2020, the overall complication rate was 16.7% (375/2249). These complications spanned different categories and a range of severities: systemic (0.9%), intracranial (2.7%), neurologic (4.6%), hardware (2.2%), and incisional (3.4%)[154]. A similar study included 96 DBS studies, including 8983 patients, investigated hardware-related complications. These included infections (5.1%), lead migration (1.6%), lead fracture (1.5%), lead failure (0.7%), neurostimulator malfunction (1.1%), and skin erosions (0.5%) [155]. No deaths were reported in either

systematic review. The risk of intracranial hemorrhage is likely higher in patients with alcohol use disorder and alcoholic liver disease due to the effects of liver disease and alcohol on platelets and other bleeding factors. Severe intracranial hemorrhage can be fatal in this patient population.

From the device brochure, Medtronic DBS therapy has a risk of adverse events related to the therapy, device, or procedure. These include: "intracranial hemorrhage, cerebral infarction, CSF leak, pneumocephalus, seizures, surgical site complications (including pain, infection, dehiscence, erosion, seroma, and hematoma), meningitis, encephalitis, brain abscess, cerebral edema, aseptic cyst formation, device complications (including lead fracture and device migration) that may require revision or explant, extension fibrosis (tightening or bowstringing), new or exacerbation of neurological symptoms (including vision disorders, speech and swallowing disorders, motor coordination and balance disorders, sensory disturbances, cognitive impairment, and sleep disorders), psychiatric and behavioral disorders (including psychosis and abnormal thinking), cough, shocking or jolting sensation, ineffective therapy, and weight gain or loss."

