12.2 Sample Size Determination

Since this study is primarily designed for the assessment of safety and feasibility, a cohort of 3 patients was decided upon per clinical judgement and experience.

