12.3 Analysis of Primary Endpoints

The primary outcomes are:

- 1) *Safety and tolerability* measured as incidence of any serious adverse effect (AE), and incidence rate and severity of AEs that are definitely, probably, or possibly related to LP DBS throughout the study duration.
- 2) *Feasibility* measured as recruitment rate and completion rates of follow-up visits and assessments throughout the study duration.

The primary outcomes will be assessed continuously throughout the study.

H1. LP DBS for severe AUD will be deemed safe and well-tolerated by DSMB.

H1.a. LP DBS for severe AUD will not result in any serious adverse effects.

H1.b. The incidence rate of AE will be similar to standard of care DBS per the DSMB judgement.

H2. LP DBS for severe AUD will be deemed feasible.

H2.a. We will successfully recruit 3 participants for the study.

H2.b. Participants will complete >80% of all study follow-up visits and assessments.

Safety, tolerability, and feasibility will be assessed continuously throughout the study. We will screen for AEs using 4 approaches: 1) patient self-report, 2) clinical evaluations (medical, neurologic, and psychiatric), 3) questionnaires (e.g., screening for depression, suicidality, anxiety, apathy, mania) and 4) neuropsychological evaluation to screen for any LP DBS effects on various cognitive domains. Every AE will be evaluated for severity, expectedness and relatedness, and reported to the DSMB.

Safety and tolerability: The study will be deemed safe and tolerable if no serious AE that are definitely, probably, or possibly related to LP DBS occur during the study and if the AE severity and rate are not higher than standard of care DBS per DSMB's assessment.

Feasibility: the study will be deemed feasible if we successfully recruit the proposed number of participants and if participants complete >80% of all study follow-up visits and assessments.

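### The primary safety rule turns zero related SAEs in three participants into a finding of safe and tolerable, with no statement of uncertainty and no defined comparator

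*Protocol*

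**What the plan says.** The rule is in section 12.3 of the Protocol and in the same section of the SAP. It has two conditions, and both must hold.

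- **SAE condition:** "The study will be deemed safe and tolerable if no serious AE that are definitely, probably, or possibly related to LP DBS occur".
- **Comparison condition:** "if the AE severity and rate are not higher than standard of care DBS per DSMB's assessment".

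The hypotheses above the rule put the same ideas in other words. H1.a says "LP DBS for severe AUD will not result in any serious adverse effects", and H1.b says "The incidence rate of AE will be similar to standard of care DBS per the DSMB judgement". Section 13.5 gives the DSMB a third version of the comparison: whether events exceed the expected grade or incidence once three participants have been assessed at six months.

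On sample size, section 12.2 says only that "a cohort of 3 patients was decided upon per clinical judgement and experience". Sections 11.2 and 12.1 provide for replacing participants who withdraw. Section 3.3 names DBS side effects in approved indications such as Parkinson's disease as the comparison, but attaches no rate. Section 8.1 reports complication rates from two systematic reviews, including 375 of 2249 patients (16.7%) overall. It does not link any of them to the rule in 12.3.

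**The concern.** The primary objective in section 3.2 is to demonstrate safety, and 12.3 fixes in advance the words that will be used if the rule is met. Nothing in 12.3 requires the count to be shown with an interval, and no level of risk is stated that the trial should be able to exclude. Section 12.4 admits that three participants give little power for the alcohol-use test. The primary safety conclusion carries no such caveat.

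Section 2.1 says that the work is meant to lead to efficacy studies. Whoever plans those could take an unqualified finding of safety as stronger evidence than it is. Section 8.1 itself expects a higher risk of intracranial haemorrhage in this population than in other DBS patients.

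The comparison condition adds little that a reader could check. Its wording varies between *similar*, *not higher* and *as expected*, and the DSMB is given no rate, event definition or denominator with which to apply it.

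**Working it through.** **Inputs.** n = 3 (section 12.2). The SAE condition is met at 0 related SAEs (12.3). The reference complication rate is 375/2249 (8.1). The documents state no confidence level for the safety count, so 95% is assumed, one-sided and two-sided. Participants are treated as independent with a common risk p.

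**1. The plan's own figure.** 375/2249 = 0.1667, which agrees with the stated 16.7%. The sample size of three has no calculation behind it, so there is nothing to reproduce.

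**2. What 0 of 3 rules out.** The exact upper limit solves (1 − p)³ = α, so p = 1 − α^(1/3).

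- One-sided 95%: 1 − 0.05^(1/3) = 0.632.
- Two-sided 95%: 1 − 0.025^(1/3) = 0.708.

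If replacement brought the number implanted to four or five, zero events would give limits of 52.7% or 45.1% (one-sided) and 60.2% or 52.2% (two-sided).

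**3. Chance of meeting the SAE condition.** P(0 of 3) = (1 − p)³.

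| True related-SAE risk p | P(0 of 3) |
|---|---|
| 5% | 86% |
| 10% | 73% |
| 30% | 0.70³ = 34% |
| 50% | 0.50³ = 13% |

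These are upper bounds on the chance of being declared safe, because the comparison condition must also be met.

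**4. For scale.** The number of participants needed for zero events to exclude a risk p is the smallest n with n ≥ ln(α)/ln(1 − p). To exclude 30%, n = 9 (one-sided 95%) or 11 (two-sided). To exclude 16.7%, n = 17 or 21. This shows how little three participants can exclude; it is not a proposal to enlarge the pilot.

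**5. The comparison condition, as an illustration only.** Suppose the 16.7% were used as a per-participant benchmark with three treated. One affected participant gives 1/3 = 33.3% (exact 95% interval 0.8% to 90.6%), which is already above 16.7%. The observed proportion would then say almost nothing about whether the true rate is higher. The plan does not specify this test. The illustration shows why the DSMB needs a named comparator and an interval.

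**The case against.** The strongest reply is that this is a labelled pilot, that any three-person study has this interval, and that the safety judgement rests with an independent DSMB that includes biostatistical expertise. The SAE condition is also strict. Events only possibly related count, and section 10 treats any inpatient hospitalisation as serious. By the figures above, a device with a 30% risk would fail the SAE condition 66% of the time. Every SAE also leads to DSMB review with the study suspended (13.5), so an interval might alter no decision during the trial.

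Most of this stands, and it limits the point. Three participants is not an error, and the rule is not lax about counting events. It does not answer the objection to the conclusion itself: a strict count of three people still cannot support an unqualified statement of safety.

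A reader might go further in four ways that the documents do not support:

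- **That the comparison condition can be met only with zero events.** This needs 16.7% as the comparator, a per-participant proportion and exactly three treated. The plan fixes none of these, leaves the matter to DSMB judgement and replaces withdrawals. The endpoint also covers related AEs of any severity, and the documents give no such rate for standard DBS.
- **That 16.7% is the only benchmark.** Section 8.1 also gives category rates and hardware-related rates.
- **That a device equal to standard DBS would fail 42% of the time** (1 − 0.579, the chance of at least one event at 16.7%). That describes a numeric test which the plan does not contain, and 16.7% is a complication rate, not an SAE rate.
- **That titration makes the rates non-comparable.** Section 6.1 does say "Stimulation intensity will be increased in small increments until we observe side effects or a voltage limit of 10V", but intensity is then reduced, and the documents do not show that rates for standard DBS exclude effects provoked during programming.

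**Conclusion.** The concern holds in a limited form. If 12.3 is followed as written, the trial may report LP DBS as safe and tolerable on data compatible with a related-SAE risk of up to 63% (one-sided 95%) or 71% (two-sided 95%). A true risk of 30% would meet the SAE condition about one time in three. These figures rest on three treated participants, a common and independent risk, and an assumed 95% level. The 34% is a ceiling on passing the whole rule, since the DSMB's judgement is also needed.

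The comparison condition is under-specified: no rate, event definition or denominator is attached to it. The documents do not allow the stronger statement that it is numerically unworkable.

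The defect lies in the stated conclusion and its reporting. It does not lie in the pilot design or in the use of a DSMB. It is worth correcting because it changes what the trial may claim and costs little.

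**What to change.** In section 12.3 of both documents:

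1. Replace the safe-and-tolerable conclusion with a modest one, such as *no safety signal that would preclude a larger study*.
2. Report the number of participants with a related SAE, and the number with any related AE, over all implanted participants, including any who withdraw and are replaced. Give each with its exact 95% interval beside the DSMB's conclusion.
3. Name the comparator source, the event definition and the denominator (participants or person-time) that the DSMB will use, and use one wording for the comparison in H1.b, the rule and section 13.5.

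The cost is some redrafting, one extra table and a more modest claim. It needs no extra patients, visits or procedures.

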12.4 Analysis of Secondary Endpoints

The secondary outcomes are:

- 1) *Alcohol use* measured as PDA, DDD, PEth, GGT at baseline and monthly after DBS implantation.
- 2) *Overall functioning* and disability measured with the WHODAS 2.0 scale at baseline and monthly after DBS implantation.
- 3) *Target engagement* measured with FDG-PET scans at 3 time points: pre-DBS baseline, post-DBS-OFF, and post-DBS-ON at 6 months.

The secondary outcome *PDA* as a measure of *alcohol use* is a proportion, collected at baseline and during follow-up and assessment visits (1 baseline and 12 monthly post-DBS measurements).

The other measures of alcohol use (*DDD, PEth, GGT*) and the overall functioning score *WHODAS 2.0* are continuous variables collected at baseline and during follow-up and assessment visits (1 baseline and 12 monthly post-DBS measurements).

Alcohol use and overall functioning

H3: LP DBS reduces alcohol use and improves overall functioning in subjects with severe AUD compared to baseline. Specifically, LP DBS increases PDA, and decreases DDD, PEth, GGT and WHODAS 2.0 score compared to baseline.

Primary analysis of H3: We will compare the baseline and 6-month time point using a paired t-test for each of the measures (PDA, DDD, PEth, GGT and WHODAS 2.0).

For PDA, the unit of analysis is the proportion of days X_{ij} in a month that participant i is abstinent during month j . To do the paired t-test, we use the two paired proportions X_{i0} (0 refers to the baseline measure) and X_{i6} (6 refers to the 6-month measure). We can use a t-test on the difference $D_i = (X_{i6} - X_{i0})$. This should be a reasonable approximation because the averages X over roughly $n = 30$

days should be approximately Gaussian. The Gaussian approximation can be improved by using the variance stabilizing transformation

$$Y_{ij} = 2 \arcsin \sqrt{X_{ij}}$$

Thus, we will do a t-test using the differences $2[\arcsin \sqrt{X_{i6}} - \arcsin \sqrt{X_{i0}}]$. With $n = 3$ participants, we have little power unless the effect is large (e.g., if PDA moves from 0.05 to 0.50).

Secondary analysis of H3: To assess the course of PDA, DDD, PhEt, GGT, and WHODAS 2.0 over the duration of the study while taking into account the repeated measures (13 measures for each participant – one at baseline and 12 post-DBS), we will use a **mixed-effects model**:

$$Z_{ij} = \mu + \alpha_i + \tau_j + \epsilon_{ij}$$

with random effect α_i for subject, a fixed time effect τ_j , and the error term (unexplained variation) ϵ_{ij} . We will have 39 measures (3 subjects times 13 measures per subject at months 0 to 12). For PDA, we will use the arcsin-transformed proportions described above to improve Gaussian approximation by stabilizing the variance.

Target engagement

H4: LP DBS will result in circuit specific target engagement measured with FDG-PET.

H4a. CGM (cerebral glucose metabolism) as measured with $[^{18}\text{F}]$ FDG-PET in pre-defined cortico-limbic ROIs will be increased in post-DBS-ON compared to pre-DBS and to post-DBS-OFF conditions.

H4b. DBS-induced increases in CGM (%) at the 6-month time point will be associated with decreased alcohol use (PDA, DDD).

Analysis of H4(a): For each ROI in each of the scan types we will run a one-way Repeated Measures (RM) ANOVA comparing CGM between the 3 time points (baseline pre-DBS, DBS-OFF, and DBS-ON at 6 months), with post-hoc comparisons of DBS-ON vs. post-DBS-OFF, and DBS-ON vs. baseline.

Analysis of H4(b): We will use Pearson's correlation to assess the relationship between changes in CGM between post-DBS-OFF and 6 months and corresponding changes in measures of alcohol (PDA, DDD).

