- Decisional impulsivity: **will be measured with the delay discounting task which** correlates with AUD severity and predicts risk of relapse [120, 121]; **outcome measure:** discounting rate.
- **Motor impulsivity:** will be measured with Stop Signal Reaction Time task (SSRT) [122, 123]. Motor impulsivity and loss of inhibitory control (**measured with SSRT**) are hallmarks of AUD [71, 124-126]; **outcome measure:** SSRT.
- **Reward processing:** will be measured with the Card Guessing Task (CGT); Reward processing is impaired in AUD[127-130]. This dysfunction is associated with abnormal neural activity recorded on EEG; the AUD-associated neurophysiological abnormalities include increased baseline spectral power (in the β - and γ -bands) and reduced event-related spectral power[131-135]. CGT has shown that reward-processing correlates with an increase in event-related spectral power in the β - and γ -bands, measured with EEG over the left ventrolateral PFC (vIPFC) [136]. To study the effects of LP DBS on the neural activity underlying reward processing in AUD, we will record brain activity with EEG while participants complete the CGT pre- and post-DBS[136, 137]; **outcome measure:** baseline and event-related spectral perturbations in the β - (15-30 Hz) and γ -bands (40-80 Hz) over the vIPFC (at electrode F7).
- **Risk taking:** will be measured with the Balloon Analog Risk Task (BART). BART measures risk taking which is predictive of alcohol-related behaviors in AUD patients [138-140]. **Outcome measure:** number of "adjusted pumps", defined as the average number of pumps on balloons, excluding those that burst [140].

4 Research Design

This will be an open-label trial to demonstrate the safety, tolerability and feasibility of LP DBS for treatment of severe AUD. The intervention is bilateral implantation of deep brain stimulation electrodes in the limbic pallidum in a single cohort of three patients. This study will be conducted at a single site (UPMC Presbyterian hospital, University of Pittsburgh). The study intervention will last from DBS implantation to the patients' 12-month follow-up evaluations (see details in section 6). Bias in research design is not a concern due to the open-label safety and feasibility nature of the study.

Since the primary outcomes of this study are safety, tolerability, and feasibility, adverse effects will be assessed on each participant at regular intervals throughout participation.

5 Human Subjects

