5.1 Subject Population

The goal is to implant DBS in 3 participants (male and female), 21-75 years old, with severe AUD and advanced liver disease (stage 3 liver fibrosis, or compensated cirrhosis/stage 4 fibrosis), living in Western Pennsylvania. Due to potential screen fails, 3-10 subjects will be enrolled (consented) and screened. We will stop enrolling subjects when 3 participants are implanted with DBS. This study will not include vulnerable populations; only adults (>21) with the capacity and competence to fulfill informed consent will be allowed to participate.

All Participants will be referred to an outpatient addiction clinic to receive standard of care AUD treatment. We will keep track of the treatments received by every participant throughout the study duration.

Inclusion/exclusion criteria were chosen to maximize both patient safety and the benefit-to-risk ratio, given the invasive nature of this study.

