1. Blood tests – complete blood count (CBC: red blood cell count, white blood cell count, platelet count), complete metabolic panel (CMP: Glucose, Calcium, Sodium, Potassium, Bicarbonate, Chloride, Blood urea nitrogen, Creatinine, Albumin, Total protein, Alkaline phosphatase, Alanine aminotransferase, Aspartate aminotransferase, Bilirubin), coagulation tests (INR, PT, PTT, platelet function test, fibrinogen activity, fibrinogen antigen, thrombin time, reptilase time, thromboelastography), pregnancy test, and makers of chronic alcohol use (blood phosphatidylethanol (PEth) and blood gamma-glutamyl transferase (GGT)). We may also check liver fibrosis blood test panel to diagnose liver fibrosis in some cases (e.g., body habitus does not allow accurate liver elastography or if there is difficulty scheduling liver elastography). Some of the blood tests may occur during the baseline evaluation days. We will repeat the following blood tests on the morning of the surgery (INR, PTT, CBC, thromboelastography).
2. Imaging – structural brain MRI (3-Tesla, with contrast) and liver ultrasound; the MRI may be deferred if already available in the EHR from the last 2 years. The liver US may be deferred if subject is already diagnosed with liver fibrosis stage 3 or 4 or if liver fibrosis blood panel is used instead. Subjects to receive a liver ultrasound in the morning are asked to omit all food and fluids (except water and medications) from midnight the night before the liver ultrasound. Subjects scanned later in the day are asked to omit food and fluids (except water and medications) for at least 4 hours prior to the liver ultrasound.
3. Clinical evaluation – medical (including EKG), neurologic, and psychiatric (including a Structured Clinical Interview for DSM-5).

If all inclusion and exclusion criteria are met after evaluation, participants will be enrolled in the study and will be scheduled for pre-DBS baseline assessment. Participants will be asked to detox and abstain from alcohol use for at least 7 days prior to the DBS surgery.

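### H3 words an uncontrolled baseline-to-6-month change as an effect of LP DBS, and no H3 contrast uses the stimulation-off month, although H4(b) needs PDA and DDD from that month

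*Protocol*

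**What the plan says.** Protocol section 12.4 and the identical SAP text set out H3: "H3: LP DBS reduces alcohol use and improves overall functioning in subjects with severe AUD compared to baseline". The primary analysis is a before-after comparison: "We will compare the baseline and 6-month time point using a paired t-test for each of the measures". The measures are PDA, DDD, PEth, GGT and WHODAS 2.0. The secondary analysis is a mixed model with a random subject effect and a fixed time effect, on 13 values per participant, "one at baseline and 12 post-DBS". The plan gives the total: "We will have 39 measures (3 subjects times 13 measures per subject at months 0 to 12".

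Several things happen between the baseline and the start of stimulation:

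- Section 7.1: "Participants will be asked to detox and abstain from alcohol use for at least 7 days prior to the DBS surgery".
- Section 5.1: "All Participants will be referred to an outpatient addiction clinic to receive standard of care AUD treatment". Treatments received are recorded, but no H3 model uses them. Section 12.1 considers only socio-demographic covariates.
- Section 1: surgery follows the baseline assessment by one to two weeks, and stimulation is switched on four weeks after implantation.

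The plan has a stimulation-off time point. Section 3.3 places an FDG-PET scan one month after surgery with DBS still off, and H4(a) compares ON with OFF for brain metabolism. H4(b) correlates "changes in CGM between post-DBS-OFF and 6 months and corresponding changes in measures of alcohol (PDA, DDD"), so it needs PDA and DDD at the OFF time point.

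Section 4 (Research Design) states: "Bias in research design is not a concern due to the open-label safety and feasibility nature of the study".

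**The concern.** H3 is an uncontrolled before-after comparison with a causal statement attached. TLFB looks back 180 days at baseline and 30 days at follow-up, so baseline PDA and DDD essentially describe drinking before detox. Any fall in drinking brought about by detox, surgery and recovery, addiction-clinic care or frequent study contact counts towards LP DBS in the H3 contrast, including any fall that occurs before the stimulator is switched on.

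The secondary objective is preliminary efficacy, and section 2.1 names later efficacy studies as the ultimate goal. A favourable H3 result would feed that decision. The plan compares ON with OFF for PET but not, under H3, for drinking, although H4(b) requires the OFF-month PDA and DDD.

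**Working it through.** **1. The plan's own count.** 3 participants × 13 measures = 39, which reproduces the stated figure.

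**2. Is the OFF month among the 13?** Appendix A puts DBS optimization on Days 50–51. As printed, the later visits at roughly monthly spacing fall on Days 80, 110, 140, 170, 200, 230, 262, 292, 322, 345, 382 and 412. That is 12 visits. Counted from Day 50.5 in 30-day months, Day 80 is month (80 − 50.5)/30 = 1.0, Day 230 is month 6.0 and Day 412 is month 12.1. The 12 visits with stimulation on therefore fill the 12 post-DBS places, and baseline is the thirteenth. Section 12.4 also describes the measures as monthly after implantation, which leaves some ambiguity, but on neither reading is an ON-versus-OFF contrast defined for H3. With the OFF month added, the count is 3 × 14 = 42.

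**3. Is the PDA/DDD baseline pre-detox?** The documents do not fix the detox date relative to the baseline interview. If abstinence began 7 to 14 days before that interview (assumption), it would cover 7/180 = 3.9% to 14/180 = 7.8% of the window. Calling the PDA/DDD baseline essentially pre-detox is fair. The same is less clear for PEth, GGT and WHODAS 2.0.

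**4. What the H3 contrast cannot show.** Take the plan's example of PDA moving from 0.05 to 0.50, and let q be PDA in the OFF month. The documents give no value for q, so the range is an assumption.

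| q (OFF month) | Month 6 − baseline | Month 6 − OFF |
|---|---|---|
| 0.05 | +0.45 | +0.45 |
| 0.20 | +0.45 | +0.30 |
| 0.35 | +0.45 | +0.15 |
| 0.50 | +0.45 | 0.00 |
| 0.75 | +0.45 | −0.25 |

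**5. How often the planned t-test would favour DBS if DBS did nothing.** On the plan's scale Y = 2 arcsin √X, a move from 0.05 to 0.50 is 1.571 − 0.451 = 1.120. With n = 3 (2 df) and two-sided 0.05 (assumed), the critical t is 4.303. A mean shift of 1.120 is significant only if the SD of the paired differences is below 1.120 × √3 / 4.303 = 0.451. The table gives noncentral-t probabilities of rejecting in DBS's favour when background change alone moves PDA from 0.05 to the value shown. The SDs are assumptions.

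| Background PDA at month 6 | SD 0.2 | SD 0.3 | SD 0.5 | SD 0.8 | SD 1.0 |
|---|---|---|---|---|---|
| 0.50 | 0.99 | 0.88 | 0.54 | 0.29 | 0.21 |
| 0.20 | 0.59 | 0.34 | 0.17 | 0.09 | 0.08 |
| 0.05 (no change) | 0.025 | 0.025 | 0.025 | 0.025 | 0.025 |

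**6. How large could background change be?** Assume that a participant who stays abstinent has PDA 1.0 and one who relapses returns to 0.05.

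- Section 2.2 gives a 1-year relapse rate of nearly 55% in primary AUD: 0.45 × 1 + 0.55 × 0.05 = 0.48.
- With 20% abstinent (assumption): 0.20 + 0.80 × 0.05 = 0.24.
- With 10% abstinent (the 90% relapse rate in section 2.2 for polysubstance use): 0.10 + 0.90 × 0.05 = 0.145.

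In this two-value scenario the t-test rarely rejects. With differences (d, 0, 0) the mean is d/3 and the standard error d/3, so t = 1. With (d, d, 0), t = 2. Both are below 4.303, so only abstinence in all three participants gives significance: 0.45³ = 9.1%, 0.20³ = 0.8%, 0.10³ = 0.1%. The high rates in step 5 need a similar shift in all three participants.

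**The case against.** The strongest defence is scope. This is a three-person open-label pilot. H3 is secondary, names its comparator, has no success rule and comes with an admission of little power. Section 4 ties its remark on bias to the safety and feasibility nature of the study. These points limit the severity. They do not remove the causal wording of H3, and low power does not protect against a biased contrast.

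Four stronger readings are tempting, and the documents do not support them.

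- A reader might infer that detox and standard care begin together with stimulation. Detox is requested at least 7 days before surgery, hence about five weeks or more before stimulation. Referral to care has no stated start date, and section 5.2 admits people already receiving AUD treatment, so care may be part of the baseline.
- A reader might infer that pre-stimulation change is not separated anywhere in the plan. H4(b) already requires each participant's OFF-to-6-month change in PDA and DDD, and section 12.1 plans individual trajectory plots. What is missing is the use of that change in H3.
- A reader might infer that an OFF value exists for every H3 measure. It is established for PDA and DDD. The schedule suggests it for PEth and GGT, but the table is broken in the text available. It is not established for WHODAS 2.0.
- A reader might set a background PDA of 0.48 against the plan's 0.50 and conclude that DBS need contribute almost nothing. The 55% rate is for primary AUD, whereas section 5.2 requires treatment-refractory disease with no sustained remission over five years. The lower values are more plausible, and under that two-value scenario the test seldom reaches significance.

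It is also fair to object that ON versus OFF is not clean. The OFF month follows requested abstinence and covers surgery and recovery. If OFF PDA is near 1.0, the contrast will be zero or negative even if stimulation is sustaining abstinence. That stands, and it is why the contrast should be descriptive.

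**Conclusion.** The point holds as a matter of attribution. H3 presents the whole change from an essentially pre-detox PDA/DDD baseline as an effect of LP DBS, while detox, surgery, referral to care and about four weeks without stimulation lie between that baseline and the start of treatment. The OFF-month PDA and DDD enter no H3 contrast and, by visit count, are not among the 39 measures.

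The size of the background change is unknown. Under the scenarios above, PDA without any DBS effect would be about 0.15 to 0.48, with the lower end more plausible for refractory patients; every figure in that range is an assumption. The documents show that the H3 contrast cannot tell these cases apart. They do not show that a positive result would be spurious. This is a worthwhile, inexpensive improvement to a secondary analysis; the primary safety and feasibility endpoints are unaffected.

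**What to change.** 1. For PDA and DDD, add the DBS-OFF month as its own time level in the H3 mixed model: 14 measures per participant, 42 in total. Do the same for PEth and GGT if the schedule confirms collection at that visit. For WHODAS 2.0, state whether an OFF value exists; if not, keep 13 measures.
2. Report 6-month minus OFF descriptively, participant by participant, beside 6-month minus baseline. State that OFF follows requested abstinence and surgery, so this contrast is likely conservative and does not isolate the DBS effect either.
3. Reword the H3 conclusion as *change from baseline during LP DBS with detox and standard AUD care*.
4. Delete the section 4 sentence on bias, or limit it so that it does not cover the efficacy endpoints.

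The cost is one extra time level, one descriptive contrast and some wording. No new visit or measurement is needed for PDA and DDD. The drawback is that low drinking just after detox may make the OFF contrast look unfavourable to DBS, which is why the caveat in item 2 must accompany it.
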